4.1 Description of Study Design

This study will use a scientifically robust, mixed-methods, two-arm cluster-randomized study design. Study subjects are not NYULH employees or patients. We will implement a tobacco use clinical reminder for outpatient psychiatrists practicing at the VA New York Harbor Healthcare System (N = 20). Half of the psychiatrists will receive a reminder that encourages the psychiatrist to offer cessation medications and referral to cessation counseling to patients interested in quitting (Opt-In Reminder). The other half will receive a clinical reminder that includes a standing NRT order and a referral to cessation counseling that will automatically generate unless the provider actively opts-out (Opt-Out Reminder). Prior to implementation of the reminders, psychiatrists in both arms will receive a one-hour training on tobacco treatment and individual education outreach to demonstrate the clinical reminder and answer questions (academic detailing).

[figure not shown]
We will use VA administrative data extracted on all patient visits with a participating psychiatrist 6 months before and after implementation to calculate the study's primary outcomes: 1) the percent of patients screened for smoking, 2) the percent of smokers prescribed a cessation medication and 2) the percent of smokers referred to counseling. To assess intervention fidelity, we will use training logs to track psychiatrist attendance at group and academic detailing trainings. Over the intervention period, we will also conduct post-visit surveys with a cluster sample of 400 patients (20 per psychiatrist) to assess psychiatrist fidelity to the 3 A's approach. At the end of the intervention period, we will conduct semi-structured interviews with 12-14 psychiatrists (6-7/arm) asking about their perceptions of the intervention components. We will also analyze implementation observations (e.g., training observations, reflection memos) and documents (e.g., meeting minutes) for implementation barriers and facilitators. At six months, we will survey the clustered 400-patient sample again to evaluate the study's secondary outcomes: 1) patient use of cessation treatment in the prior 6 months and 2) self-reported 7-day abstinence at 6 months.

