5.1 Inclusion Criteria

Study subjects are not NYULH employees or patients. In order to be eligible to participate in this study, an individual must meet all of the following criteria:

- A. Psychiatrists
 1. Works in outpatient psychiatry at the VA New York Harbor Healthcare System and has no plans to leave in the next 6 months
- B. VA patient Post-Visit Survey Population (NOT NYULH Patients)
 1. Had a visit with a psychiatrist included in the study
 2. Current smoker

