5.2 Exclusion Criteria

An individual who meets any of the following criteria will be excluded from participation in this study:

- A. Outpatient Psychiatrists
 1. None
- B. Patient Post-Visit Survey Population
 1. Non-English speaking

CONFIDENTIAL

5.3 **Vulnerable Subjects**

Outpatient Psychiatrists (VA staff) will be included in this study.

5.4 **Strategies for Recruitment and Retention**

Data Sources

Method of Subject Identification and Recruitment

A. Psychiatrists (n=20)

- a. All outpatient psychiatrists at the VA NYHHS (based on administrative records) will be identified and notified of the study via a regular department meeting. Psychiatrists will have the opportunity to ask questions one-on-one with [name] before deciding whether to participate. Psychiatrist turn-over is low at the facility; however, during recruitment we will ask psychiatrists if they plan to leave in the next 6 months and only enroll those who have no plans to leave.
- b. *Semi-Structured Interview Recruitment:* We will use two methods to recruit psychiatrists for interviews. First, we will have a sign-up sheet during the training sessions and academic detailing sessions requesting volunteers. If we do not obtain our desired sample size using this method, we will employ the second approach of sending an email (with up to two follow-up emails and/or calls) notifying psychiatrists of the interview portion of the study with instructions on how to contact study staff if interested. A trained interviewer will follow an interview guide with a set of pre-specified questions and follow-up probes. All interviews will be audio-taped.

B. Patient Post-Visit Survey Population (n=400)

- c. To identify and recruit patients for the surveys, we will use the EHR to identify a list of patients seen by a participating psychiatrist on the day we run the EHR query. We will take a random selection of 5-10 male patients (depending on response rate) and all female patients (to increase representativeness of women) per psychiatrist at each monthly assessment point to reach out to for a survey. We aim to complete post-visit surveys with 20 patients per psychiatrist over the intervention period (N=200/arm).

AIM 1 Measures: Tobacco Screening, Prescriptions and Treatment Referrals

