Table 2 on page 9 of the protocol outlines our measures, data sources and data collection schedule for the study. Our assessment plan for Aim 1 is to use VA administrative data to estimate and compare the effect of the Opt-Out versus Opt-In treatment systems on the percent of all patients screened and treated for tobacco use by their psychiatrist during the study's intervention period. The VA uses a fully electronic health record system that documents diagnostic and procedural data from all outpatient and inpatient encounters. The VA's Informatics and Computing Infrastructure (VINCI) allows VA-affiliated researchers to query encounter data and has data analysts available to assist investigators with data selection. We will work with VINCI programmers to identify all patients seen by a participating psychiatrist in the six months before and after implementation of the clinical reminder. We will then ask VINCI programmers to calculate the percent of these patients who were screened for tobacco use by the psychiatrist, and then among smoking patients, the percent prescribed at least one cessation medication and the percent who were referred to the local cessation program.

CONFIDENTIAL

This material is the property of the NYU School of Medicine and NYU Langone Health. Do not disclose or use except as authorized in writing by the study sponsor

AIM 2 Measures: Fidelity, Provider Perceptions, and Implementation Barriers and Facilitators

Intervention Fidelity: We will use training logs and post-visit patient surveys to assess fidelity to the interventions:

1. **Training Logs:** We will log all training activities to capture the proportion of participating psychiatrists who attended the training sessions and received an academic detailing visit, and the content and length of the academic detailing visits.
2. **Post-Visit Patient Surveys:** Once a month during the 6-month intervention period we will survey a random sample of patients seen by a participating psychiatrist within 24 hours of their visit. The survey will ask patients whether their psychiatrist asked them about their smoking, and offered NRT and counseling, as well as the patient's sociodemographics, smoking behavior, cessation treatment use, and motivation to quit.

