3. Semi-structured Provider Interviews: Guided by the Proctor and CFIR models, we will conduct semi-structured interviews with 12-14 psychiatrists (6-7 per arm) assessing their views on the appropriateness, acceptability and sustainability of the intervention components, as well as how the clinic’s *inner setting* (e.g., culture, norms, workflow compatibility with the intervention), *outer setting* (e.g., VA policies, psychiatric professional associations), *psychiatrist characteristics* (e.g., beliefs about the intervention), and the *implementation process* (e.g., how providers were informed, who championed the intervention) may impact their views on appropriateness, acceptability and sustainability. We will also ask psychiatrists for their insights into challenges and successes encountered during their participation in the intervention components.

AIM 3 Measures: Patient Use of Cessation Treatment and Self-Reported Abstinence

We will also assess patient use of cessation treatment and tobacco abstinence 6 months after seeing a participating psychiatrist in the two arms. For this aim, we will conduct a follow-up telephone survey with the 400 cluster-sampled patients who completed a post-visit survey during the intervention period. The follow-up survey will ask patients to indicate whether they used a list of tobacco treatments in the prior 6 months, including all FDA-approved cessation medications, in-person cessation counseling, telephone cessation counseling, and a mobile texting cessation service. Consistent with guidelines for measuring abstinence in pragmatic trials, the survey will also assess 7-day point prevalence abstinence.⁴⁸ Using methods that we have successfully used on prior research, we will make up to 10 attempts at different times of the day and month to reach patients by phone for a follow-up survey. Telephone non-respondents will be sent a survey in the mail with a pre-paid return envelope.

Other Measures: Patient Characteristics

Our patient surveys will collect additional information, including sociodemographics (age, gender, marital status, race/ethnicity, income), attitudes toward tobacco treatment using the *Attitudes Toward Nicotine Replacement Therapy Scale*⁴⁹ adapted to ask about NRT and counseling, quitting self-efficacy using the *Smoking Self-Efficacy Questionnaire*,⁵⁰ motivations to quit using a 0-10 scale, and smoking status and history using questions from the California Tobacco Survey.⁵¹

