7.1.1.4 Post-Visit Patient Survey

Patient PHI, including names, phone numbers, mental and physical health information, and tobacco-related measures will be obtained through CPRS and patients who see a participating psychiatrist. Once a month during the 6-month intervention period we will survey a random sample of patients seen by a participating psychiatrist within 24 hours of their visit. The survey

CONFIDENTIAL

will ask patients whether their psychiatrist asked them about their smoking, and offered NRT and counseling, as well as the patient's sociodemographics, smoking behavior, cessation treatment use, and motivation to quit.

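### Can monthly EHR queries yield 20 surveyed smokers per psychiatrist?

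*Combined protocol and SAP*

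**What the plan says.** Section 5.4 builds the survey list from one day's clinic: "we will use the EHR to identify a list of patients seen by a participating psychiatrist on the day we run the EHR query". From that list staff take a "random selection of 5-10 male patients (depending on response rate) and all female patients" for each psychiatrist at every monthly point. The goal follows: "We aim to complete post-visit surveys with 20 patients per psychiatrist over the intervention period (N=200/arm".

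The Aim 2 measures in Section 5.4 give the frequency: "Once a month during the 6-month intervention period we will survey a random sample of patients". Section 7.1.1.4 repeats it with the contact window: "we will survey a random sample of patients seen by a participating psychiatrist within 24 hours of their visit". Eligibility in Section 5.1 includes "Current smoker", and Section 5.6 counts the cohort as 400 smokers, with recruitment ending at approximately that number. Aim 3 then relies on a "follow-up telephone survey with the 400 cluster-sampled patients who completed a post-visit survey during the intervention period".

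The only workload figure is in Section 9.3: about 4,000 unique patient visits over 6 months for 20 psychiatrists. It is used there to power the proportion of patients prescribed a cessation medication.

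**The concern.** The natural first reading of Sections 5.4 and 7.1.1.4 is one query day per psychiatrist per month, so six days in all. The 24-hour window stops staff from looking back over earlier weeks to lengthen a list. If each psychiatrist has 200 visits in 6 months, a single day lists fewer than two patients. From so short a list one cannot draw 5-10 men, and six such lists do not contain 20 patients, let alone 20 smokers who answer. Because Aim 3 takes its sample from surveys completed during the intervention period, later recruitment could not make up the difference.

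At stake would be the patient-reported part of the fidelity assessment (Aim 2) and both secondary outcomes (use of cessation treatment and 7-day abstinence), which would rest on far fewer than 400 smokers.

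**Working it through.** **Inputs from the documents.** 20 psychiatrists, 10 per arm; 4,000 over 6 months; 10% control rate; ICC 0.05-0.15; 5% type I error (taken as two-sided); 80% power (Section 9.3). Six monthly points, 5-10 men plus all women per point, target 20 per psychiatrist (Section 5.4).

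**Assumptions, not in the documents.** 120-130 working days in 6 months; 30-40% smokers; 50-70% response; clinic days per week; visits per patient.

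**1. The plan's own figures.** 20 x 20 = 400, or 200 per arm, as stated. For Section 9.3, cluster size is 4,000/20 = 200.
- ICC 0.05: design effect 1 + 199 x 0.05 = 10.95; effective n per arm 2,000/10.95 = 182.6; detectable rate 20.55% (pooled z), stated as 21%.
- ICC 0.15: design effect 1 + 199 x 0.15 = 30.85; effective n 2,000/30.85 = 64.8; detectable rate 29.4% (pooled) or 28.95% (unpooled), stated as 29%.

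So 4,000 is the number of analysis units, at 200 per psychiatrist. This does not show that it is also the total number of visits.

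**2. The literal reading.** 200/130 = 1.54 and 200/120 = 1.67 visits per day. Six query days list 9.2-10.0 per psychiatrist; times 20, that is 185-200 in all.

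**3. The draw against that list and against the target.** To see 5-10 men on an average day over 126 days would take 630-1,260 visits by men (5 x 126, 10 x 126), against 200 visits in all. The draw does fit the target: 20/6 = 3.33 completed surveys a month, which is 3.33/10 = 33% to 3.33/5 = 67% of the men contacted. Whoever wrote Section 5.4 therefore had longer lists in mind than step 2 gives.

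**4. Other readings.** Listed = 200 x v x 6/D, where v is visits per counted unit and D is clinic days in 6 months (126 at five a week, 52 at two, 26 at one). Completed = listed x smoker share (0.3-0.4, or 1 if all are smokers) x response (0.5-0.7).

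| 4,000 counts | v | D | Listed | Completed |
|---|---|---|---|---|
| Visits | 1 | 126 | 9.5 | 1.4-2.7 |
| Visits | 1 | 26 | 46.2 | 6.9-12.9 |
| Patients | 3 | 126 | 28.6 | 4.3-8.0 |
| Patients | 3 | 52 | 69.2 | 10.4-19.4 |
| Patients | 3 | 26 | 138.5 | 20.8-38.8 |
| Smokers | 3 | 126 | 28.6 | 14.3-20.0 |
| Smokers | 4 | 126 | 38.1 | 19.0-26.7 |
| Smokers | 2 | 52 | 46.2 | 23.1-32.3 |

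All rows keep one query day a month, timed to a clinic day. The range is 1 to 39, and the last four rows reach 20 within their range.

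**5. What a shortfall would cost.** Illustrative 95% half-width for the arm difference, assuming 15% abstinence and borrowing the ICC range that Section 9.3 uses for prescribing: 1.96 x sqrt(2 x 0.15 x 0.85/n_eff), with n_eff = 10m/(1 + (m-1) x ICC), before loss to follow-up.

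| m per psychiatrist | ICC 0.05 | ICC 0.15 |
|---|---|---|
| 20 | 9.8 points | 13.7 points |
| 10 | 11.9 points | 15.2 points |
| 3 | 19.0 points | 20.6 points |

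Halving the sample costs 11.9 - 9.8 = 2.1 or 15.2 - 13.7 = 1.5 points. The large loss needs about 3 per psychiatrist.

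**6. What a fixed repeat-query rule would cost.** On the visits reading, meeting 3.33 surveys a month needs 3.33/(1.587 x 0.4 x 0.7) = 7.5 to 3.33/(1.587 x 0.3 x 0.5) = 14.0 query days, out of 126/6 = 21 working days.

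**The case for a change.** The strongest argument for a change is step 3. The clash between a one-day list and a draw of 5-10 men needs no assumption about smoking prevalence or response, only the visits reading and an even load. Section 9.3 does shorten its phrase to 4,000 visits in both power statements. No section says that queries are timed to clinic days or repeated within a month, and followed to the letter the wording could leave very few patients per cluster.

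What stands is that two details are unstated: the number of query days in a monthly point, and the unit of the 4,000. The step from there to a shortfall does not stand. The outcome powered in Section 9.3 is defined per patient and, in Sections 4.1, 4.2.1 and 9.2.2, among smokers. Completing the reminder switches it off for nine months (Sections 6.1.1 and 6.1.2), longer than the 6-month window, so a patient who completes it does so once. Both points fit a count of patients or smokers at least as well as a count of all traffic, and repeat visits would then raise the daily load above 1.5-1.7. The query-day sentence secures contact within 24 hours; it does not limit a monthly point to one run or put all psychiatrists on one day. Finally, a draw that presupposes longer lists is evidence that longer lists were meant, not that the target is wrong.

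**Conclusion.** No change is needed. The figure of 9-10 listed patients is correct only if the 4,000 is total traffic, days are evenly loaded and each month has exactly one query day. The documents support none of these firmly and give no visits per patient, clinic days, smoker share or response rate with which to test them. With assumed values, completed surveys run from about 1 to about 39 per psychiatrist, so no stated figure is shown to be out of reach.

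The gap is one that staff fill sensibly. They work to a count of 20 per psychiatrist, the size of the draw already varies with response, smokers can be identified in CPRS beforehand (Section 10.3.2), and a short list on one day is an obvious reason to run the query on another. The consequences are also limited: the three primary outcomes use administrative data, the plan claims no precision for the 400, and even half the sample would widen the illustrative interval by only about 2 points on either side. Writing in a repeat-query rule sized on the least favourable reading could commit callers to 14 of 21 working days a month for a shortfall that may not exist.

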AIM 2: Assess intervention fidelity, provider perceptions, and barriers and facilitators to implementation: For intervention fidelity, we will use descriptive statistics to summarize the patient post-visit survey data to calculate the proportion of patients seen by a participating psychiatrist in each study arm who were asked about smoking, offered medications, offered counseling referral, and (among those offered) the proportion of patients who accepted medications and referral. We will also summarize training fidelity logs (the proportion of psychiatrists who attended the trainings and received an academic detailing session). To assess provider perceptions quantitatively, we will summarize provider survey data using descriptive statistics (means, standard deviations) to understand providers' attitudes and beliefs regarding treating their patients for tobacco. For our qualitative data analysis (interviews, observations, reflection memos, meeting minutes), we will use a three-step coding process for each data source. First, two investigators will individually read a sub-sample of data (e.g., 3 interviews) to identify preliminary inductive codes, then meet to achieve consensus on coding the sub-sample and create the first draft of a code book. Second, the investigators will individually apply the codebook to a second sub-sample of data, and meet to achieve coding consensus on the second sub-sample to create final codebook for the data source. Third, once all data are coded, the investigators will meet to complete more focused coding to identify code clusters, relationships among codes, and common themes. Once all data sources are coded, we will also use group consensus meetings to look for themes across the four main data sources.

AIM 3: Estimate the effect of the Opt-Out Reminder versus the Opt-In Reminder on the use of cessation treatment and self-reported abstinence among mental health patients who smoke: We will use a similar analytic approach as in Aim 1. We will first categorize each patient as: (1) having achieved or not achieved 7-day abstinence 6 months after their psychiatry visit and (2) having used or not use any type of cessation treatment in the 6 months after their visit. This will estimate use of treatment and abstinence rates for each study arm. We will use GLMMs to compare these two outcomes between groups. Sensitivity analyses will be used to evaluate the impact on results

CONFIDENTIAL

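### The post-visit survey takes all women but only some men, and the plan reports simple proportions of patients seen; wherever men are sub-sampled, women are over-represented

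*Combined protocol and SAP*

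**What the plan says.** Section 5.4 (Patient Post-Visit Survey Population) draws the sample from "a list of patients seen by a participating psychiatrist on the day we run the EHR query". From that list, each psychiatrist contributes a "random selection of 5-10 male patients (depending on response rate) and all female patients (to increase representativeness of women" at every monthly assessment point. The target is stated as follows: "We aim to complete post-visit surveys with 20 patients per psychiatrist over the intervention period (N=200/arm".

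The Aim 2 measures, also in Section 5.4, describe the same survey more briefly: "Once a month during the 6-month intervention period we will survey a random sample of patients seen by a participating psychiatrist". Section 7.1.1.4 repeats this. Neither place mentions the selection by sex. Section 5.1 limits survey eligibility to "Current smoker".

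For analysis, Section 9.2.2 (Aim 2) says that "we will use descriptive statistics to summarize the patient post-visit survey data to calculate the proportion of patients seen by a participating psychiatrist" in each arm who were asked about smoking or offered treatment, with acceptance reported among those offered. The Protocol Summary says the same. For Aim 3, which follows up the same patients, Section 9.2.2 adds: "This will estimate use of treatment and abstinence rates for each study arm".

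The plan nowhere mentions selection fractions, sampling weights, reporting by sex or standardisation to the sex mix of patients seen. The sensitivity analyses in Section 9.2.2 deal with missing data and dropout only.

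**The concern.** Taking every woman and a subset of men is a legitimate way to gain precision for women. It also makes the chance of selection depend on sex. A pooled simple proportion then describes the sample, not the patients seen. If men and women differ in how often they are asked, offered or accept treatment, the pooled figure moves towards the women's value. The stated reason for the rule is representativeness, yet without weights or stratification the pooled figure becomes less representative.

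At stake are the arm-level fidelity and acceptance proportions of Aim 2, and the arm-level treatment-use and abstinence rates of Aim 3. These are descriptive levels that readers will take at face value. The selection fractions may be hard to reconstruct later if the counts are not logged, or the lists not kept, when each query is run.

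**Working it through.** **The plan's own figures.** 20 psychiatrists x 20 surveys = 400, and 10 x 20 = 200 per arm. Both agree with Section 5.4.

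**Inputs for the bias.** The documents give none of these, so they are assumptions:
- f, women's share of eligible patients: 10-20%
- r, fraction of listed eligible men who are taken: 50-70%
- d, difference between the sexes in the rate of an item: 10 points

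**Formulas.** Women's share of the sample is w = f / (f + (1 - f) x r). The bias of the simple proportion, in absolute size, is (w - f) x d. Inverse-selection weights are 1 for women and 1/r for men. The Kish factor, which gives the precision cost of weighting, is (f + (1 - f) x r) x (f + (1 - f)/r).

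| f | r | w | Bias per 10-point difference | Kish factor | 200 per arm acts like |
|---|---|---|---|---|---|
| 0.10 | 0.7 | 0.10/0.73 = 13.7% | 0.4 points | 1.01 | 198 |
| 0.10 | 0.5 | 0.10/0.55 = 18.2% | 0.8 points | 1.05 | 191 |
| 0.20 | 0.7 | 0.20/0.76 = 26.3% | 0.6 points | 1.02 | 196 |
| 0.20 | 0.5 | 0.20/0.60 = 33.3% | 1.3 points | 1.08 | 185 |

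The last column is before any allowance for clustering. If r = 1 or d = 0, the bias is zero; if r = 1, the Kish factor is also 1.

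**Example with assumed rates.** Take f = 0.20, r = 0.5, and 70% of men and 60% of women asked about smoking.
- True proportion: 0.8 x 70 + 0.2 x 60 = 68.0%.
- Simple sample proportion: (2/3) x 70 + (1/3) x 60 = 66.7%, which is 1.3 points low.
- Weighted: ((1/3) x 60 + (2/3) x 2 x 70) / (1/3 + 4/3) = 68.0%.

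For scale, the standard error of a 68% proportion on 200 patients is sqrt(0.68 x 0.32 / 200) = 3.3 points before clustering.

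**Does the male limit bind?** Section 9.3 gives about 4,000 visits. That is 4,000/20 = 200 per psychiatrist, or 200/6 = 33 per month. Over an assumed 130 working days it is about 1.5 a day, at which every man would be taken. But six query days at 1.5 give only about 9 patients, short of the 20 completed surveys wanted per psychiatrist. Typical query-day lists must therefore be longer than this average if the target is to be met, and their length cannot be fixed from the documents.

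**What each r implies.** With 5-10 men taken, r = 0.7 needs about 7-14 eligible men on one psychiatrist's list for one day (5/0.7 to 10/0.7). r = 0.5 needs 10-20, and r = 0.3 needs 17-33.

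**The case against.** The strongest reply is that the limit may seldom bind. It applies to one psychiatrist's list for one day, and the volume in Section 9.3 points to short lists. On any day when all men are taken, both sexes have selection probability 1 and the simple proportion is right. This stands as a limit on the size of the problem. It does not remove it: the plan's rule presupposes lists long enough for a random draw of men to matter, and the survey target cannot be met at the average daily volume.

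Other points that stand:
- The absence of weights is inferred from silence; the plan describes only simple summaries.
- Calling the sample random in the Aim 2 measures and Section 7.1.1.4 is no contradiction. A sample stratified by sex, with one stratum taken whole, is still random, and the recruitment text in Section 5.4 supplies the detail.
- Aim 2 fidelity is descriptive, with no test or decision rule. The three primary outcomes use EHR data on all patients seen and are untouched.
- Gender is already collected in the patient surveys (Section 5.4, Other Measures), so reporting by sex needs no design change.

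**Conclusion.** The mismatch is real but conditional and small. Where men are sub-sampled, the pooled Aim 2 proportions, and likewise the Aim 3 arm-level rates, over-represent women relative to the population named. Under the assumptions above (women 10-20% of eligible patients, 50-70% of men taken), the bias is about 0.4 to 1.3 points per 10-point sex difference. It is zero where every man is taken or the sexes do not differ. This merits an inexpensive improvement and does not threaten the trial's main result.

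Three stronger readings are tempting, and the documents do not support them:
- **A bias of around 5 points.** This needs, for example, women at 20%, a 20-point sex difference and only 30% of men taken: (0.20/0.44 - 0.20) x 20 = 5.1. A 30% fraction means 17-33 eligible men on a single day's list, which is half to all of the roughly 33 visits a month that Section 9.3 implies per psychiatrist.
- **Unequal bias in the two arms.** The same rule runs in both, and Section 4.1 stratifies randomisation by panel size and number of patients who smoke, the likely drivers of list length. Unequal bias is possible but not shown.
- **Sex-dependent selection as the reason patients of psychiatrists with small panels count for more.** That tilt comes mainly from the fixed 20 surveys per psychiatrist. Roughly equal numbers suit a survey that Section 4.1 says is meant to assess psychiatrist fidelity.

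Separately, because eligibility requires current smoking, even a correctly weighted figure describes smokers seen, not all patients seen.

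**What to change.** 1. For each psychiatrist and query day, log the number of eligible and of selected patients, separately for men and women.
2. Report Aim 2 proportions and Aim 3 arm-level rates weighted by the inverse of the selection fraction, or stratified by sex.
3. Include sex as a covariate in the Aim 3 GLMMs. This does not replace step 2 for the arm-level rates, because a covariate alone does not restore the population mix.
4. State the target population in Section 9.2.2 and the Protocol Summary as smokers seen by a participating psychiatrist.

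The cost is two counts per query for each sex's list and selection, a few lines of analysis text, and a small loss of precision: Kish factor 1.01 to 1.08 over the assumed range, and none if all men are taken. Adding sex to the models costs almost nothing, since it is already collected.

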Table 2: Measures, Data Source and Collection Tool

Measures	Data Source	Timing	Aim
PRIMARY OUTCOMES			

CONFIDENTIAL

This material is the property of the NYU School of Medicine and NYU Langone Health. Do not disclose or use except as authorized in writing by the study sponsor

Proportion of patients screened for smoking	EHR	6 months pre and post implementation	1
Proportion of smokers prescribed cessation medication	EHR	6 months pre and post implementation	1
Proportion of smokers referred for counseling	EHR	6 months pre and post implementation	1
SECONDARY OUTCOMES			
Patient use of cessation treatment	Patient post-visit survey and telephone follow-up survey	6 months before and after post-visit survey	3
Patient self-reported 7-day abstinence	Patient follow-up survey	6 months after post-visit survey	3
PROVIDER PERCEPTIONS			
Provider perceptions of the intervention	Provider interviews Training observations	6 months post-implementation Training period	2
Provider attitudes toward treatment, self-efficacy toward treatment, ⁴⁶ treatment norms ⁴⁶ , motivation ⁷ and intention to treat ⁴⁶	Provider Survey	Baseline and 6 months post-implementation	2
IMPLEMENTATION BARRIERS AND FACILITATORS			
Barriers/facilitators toward implementation of the intervention components	Provider interviews Study observation logs	6 months post-implementation Intervention period	2

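### The follow-up treatment-use question is described as looking back 6 months from the answer, while the Aim 3 outcome runs 6 months forward from the visit, so the two windows separate for late respondents

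*Combined protocol and SAP*

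**What the plan says.** The documents describe the treatment-use measure in two ways.

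- **Looking back from the survey.** Section 4.1 lists the secondary outcome as "patient use of cessation treatment in the prior 6 months", collected in a survey at six months. The Aim 3 measures in Section 5.4 describe the item in the same way: "The follow-up survey will ask patients to indicate whether they used a list of tobacco treatments in the prior 6 months".
- **Looking forward from the visit.** Section 9.2.2 (Aim 3) classifies each patient as "having used or not use any type of cessation treatment in the 6 months after their visit". Objective 3 in the Protocol Summary uses the same definition. Table 2 gives the timing as "6 months before and after post-visit survey". Because the post-visit survey samples patients "seen by a participating psychiatrist within 24 hours of their visit", anchoring to that survey or to the visit is practically the same.

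On follow-up effort, Section 5.4 says "we will make up to 10 attempts at different times of the day and month to reach patients by phone for a follow-up survey". Patients not reached by phone are then mailed a survey. No earliest or latest acceptable date, return window or rule for late answers is given. Section 9.2.2 makes complete-case analysis primary for Aim 3, and its sensitivity analyses concern missing data and dropout.

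**The concern.** A lookback of 6 months equals the 6 months after the visit only if the patient answers at exactly 6 months. Repeated calls followed by mail leave room for later answers, and mailed answers come last because mail starts only after the calls have failed. For a late respondent the weeks straight after the visit fall in a gap: they come after the post-visit survey and before the follow-up window opens, so neither survey covers them.

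Under Section 6.1.2 the opt-out reminder places the NRT order and the counseling consult when a smoker is identified at a visit. Where that happens at the sampled visit, the lost weeks are those in which use prompted by the default would be expected to begin. A late respondent with only early use is not missing. That patient enters the complete-case analysis as a non-user, and the planned missing-data sensitivity analyses would not detect it. At stake is one of the two secondary patient outcomes.

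**Working it through.** The plan gives no power or sample-size figure for Aim 3 (Section 9.3 covers only the prescription outcome), so there is no stated figure to reproduce. The check is date arithmetic followed by an illustration.

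**1. Window shift.** Take 6 months as 182.6 days. The outcome covers days 0 to 182.6 after the visit. An answer d days past the 6-month mark covers days d to 182.6 + d. The share lost at the start is d / 182.6, and an equal period is added at the end. The delays below are assumed, since the documents give none.

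| Delay d (days) | Share of outcome window lost |
|---|---|
| 0 | 0% |
| 14 | 14/182.6 = 8% |
| 28 | 28/182.6 = 15% |
| 60 | 60/182.6 = 33% |
| 90 | 90/182.6 = 49% |

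**2. Who is misclassified.** Losing part of the window does not by itself change a patient's score. A late respondent is wrongly scored only if (a) all use of every listed treatment fell in the lost days, giving a false no, or (b) the first use came after month 6, giving a false yes.

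**3. Effect on the difference.** Let u be true use in an arm, L the share answering late, e the share of users whose only use fell in the lost days, and g the share of non-users who first used treatment in the added days. Assume lateness is unrelated to use. Then

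observed use = u(1 − L·e) + (1 − u)·L·g.

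If L, e and g are equal in both arms, the difference is multiplied by 1 − L(e + g). Error (b) raises both rates, but when equal across arms it narrows the difference further. It offsets error (a) in the comparison only if it is more common under Opt-Out.

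**4. Illustration with g = 0.** All inputs are assumed. True use is 30% vs 20%, a difference of 10.0 points.

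| Late share L | e, Opt-Out / Opt-In | Observed rates | Difference |
|---|---|---|---|
| 10% | 10% / 10% | 29.7% vs 19.8% | 9.9 |
| 25% | 20% / 20% | 28.5% vs 19.0% | 9.5 |
| 25% | 40% / 20% | 27.0% vs 19.0% | 8.0 |
| 50% | 40% / 20% | 24.0% vs 18.0% | 6.0 |

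**5. Ratio scales.** Assume true use of 35% vs 20%, g = 0 and equal loss in both arms. With L = 25% and e = 30%, the share of users missed is 0.25 × 0.30 = 7.5%, and the difference goes from 15 to 15 × 0.925 = 13.9 points. With L = 50% and e = 50% the share is 25%, and the difference is 15 × 0.75 = 11.3 points. The risk ratio stays at 1.75 (32.375/18.5 and 26.25/15). The odds ratio goes from (0.35/0.65)/(0.20/0.80) = 2.15 to 2.11 and 2.02 respectively. If the GLMM uses a logit link (the link is not stated), equal loss therefore moves the estimate little.

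**The case against.** The strongest reply is that the documents describe one nominal interval. Section 4.1 places the survey at six months, Section 5.5 gives patients 6 months of participation, and Table 2 ties the measure to the post-visit survey. At a 6-month interview the two wordings mean the same thing. Section 5.4 also paraphrases the item. The follow-up questionnaire is not among the documents, and the appendix list names only the post-visit survey, so the actual item may already refer to the visit. Nothing says that anyone answers at 7 or 8 months: "we will make up to 10 attempts at different times of the day and month" gives neither a start date nor a duration.

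These points limit size and confidence. They do not remove the mismatch, because the stated recall period and the analysed period agree only for on-time answers and no rule keeps answers on time.

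A reader might also infer that the survey systematically misses the period in which the default acts. The documents do not support that. Completing the reminder switches it off for 9 months, and patients are sampled from visits throughout the 6-month period, so the order may have fired at a visit before the sampled one. Counseling follows later contact by program staff (Section 6.1.1) and need not cluster at the visit.

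**Conclusion.** The point holds as an inconsistency between the described recall window and the analysed outcome, with misclassification of some late respondents as its consequence. The likely effect is a modest attenuation of the secondary treatment-use comparison. The size of the window shift follows from the delay alone (about 15% of the window at 28 days, about 33% at 60 days). The size of the bias cannot be derived: the late share, the timing of use and the arm rates are all assumptions, and the illustrations run from negligible (9.9 against 10.0 points) to 6.0 against 10.0. The larger figure needs half the respondents to be late and early-only use to be twice as common under Opt-Out. A reader might take it as a forecast of serious bias, but the documents give no evidence of a difference between arms in lateness or timing of use. The primary outcomes come from administrative data and are unaffected. Low severity, moderate confidence: a cheap improvement, best made before follow-up starts, because weeks that were not asked about cannot be recovered from completed surveys.

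**What to change.** 1. Word the phone and mail item as *since your visit with your psychiatrist on [date]*. This restores the lost early days whatever the delay.
2. Record the response date, and state the earliest and latest acceptable dates for the follow-up survey. A closing date also limits how much use after month 6 can be counted, which the anchored wording alone does not remove.
3. Add a sensitivity analysis limited to on-time responses, noting that on-time and late respondents may differ in other ways.
4. Give one definition of the window in the Protocol Summary (Objective 3), Section 4.1, the Aim 3 measures in Section 5.4, Table 2 and Section 9.2.2. If the questionnaire is already anchored to the visit, the protocol text should say so.
5. Optionally, ask the month of first use so that use starting after month 6 can be separated. This is a harder recall task and is not essential.

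The cost is one item's wording, one date field and a short analysis. The downside is slightly longer recall for late respondents. No sample-size figure changes.
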